# 9.12. Stopping Rules

### 9.12.1. Subject Stopping Rules

Any event of DKA or severe hypoglycemia will result in withdrawal of subject from study, if it is related to the use of AHCL Auto Mode.

Version D

# 9.12.2. Stopping Rules for Entire Study

During the study period, the following steps will be taken for:

- Unanticipated Adverse Device Effects (UADE) •
- Device related Diabetic Ketoacidosis (DKA) •
- Device related Severe hypoglycemia •
- 1. Site will notify the sponsor within approximately 24 hours of receiving knowledge of the event.
- 2. Sponsor will notify Food and Drug Administration (FDA) within approximately 72 hours of knowledge of the event and provide updates to those agencies as information becomes available.
- 3. Clinical Events Committee (CEC) is to review the event within 7 days from the time that the sponsor is notified.
- 4. CEC will provide recommendation to the sponsor on the following:
  - a) If enrollment and study may continue
  - b) If enrollment should be stopped; enrolled subjects are still allowed to continue in study
  - c) If the entire study must be stopped, including subjects who have already received study devices.

Page 69 of 118

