#### 3.2. Purpose

The purpose of this study is to evaluate the safety of the Advanced Hybrid Closed Loop system (AHCL) in type 1 diabetes adult and pediatric subjects in a home setting. In addition, during the continued access period, all remaining subjects will receive the 780G insulin pump system to evaluate subject safety.

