#### 4.2.3. Safety Endpoint – During Study Period and Continued Access

- Serious Adverse Events (SAE)
- Serious Adverse Device Effects (SADE)
- Unanticipated Adverse Device Effects (UADE)
- Incidence of Severe Hypoglycemia
- Incidence of DKA

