## 5. Study Design

10813115DOC

This study is a multi-center, single arm study in insulin-requiring adult and pediatric subjects with type 1 diabetes. The study period will be approximately 90 days long. It will be followed by a continued access period, during which subjects who have completed the entire study period will be given the opportunity to continue using investigational study devices until those devices are approved by the FDA for commercial use and are commercially available. They will be provided with a revised consent form and will sign it prior to continuing. Subjects who have already completed the study period will be given the opportunity to re-enter the study, if they elect to continue using the system. They will also sign the revised consent form, if required by IRB.

A total of up to 350 subjects (aged 7-75) will be enrolled at up to 30 investigational centers in the US in order to achieve the following:

- N=125 subjects 14-75 years of age with type 1 diabetes who will complete the study
- N=125 subjects 7-13 years of age with type 1 diabetes who will complete the study

Staged enrollment:

• Subjects 7-13 years of age may be enrolled after N=15 subjects 14 -75 years with type 1 diabetes have finished 30 days of the study period. The Data Monitoring Committee (DMC) will review the subjects' data. Enrollment of subjects 7-13 years of age may begin after DMC approval.

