#### **Study Period:**

Having met all criteria, subjects will proceed to the study period, which begins at Visit 5. All subjects will continue using the study pump and will use Auto Mode for 90 days during the study period.

Subjects should use the system in Auto Mode at all times. If subjects are exited from Auto Mode, they should try to mitigate and return to Auto Mode as soon as possible. During times when subjects are not able to use Auto Mode, they should use the remaining SmartGuard™ features (i.e. Suspend before Low).

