#### **Continued Access Period expansion:**

During the continued access period, all participating subjects will transition from the 670G system, version 4.0 AHCL, to the 780G system which features Bluetooth® connectivity. The CGM used with 780G will be Guardian™ 4 Transmitter with the Guardian™ Sensor (4).

Subjects will continue to use the 780G system at home until the sponsor notifies sites to end subjects' study participation.

The MiniMed™ Clinical App and the Medtronic CareLink™ Clinical App will be used by subjects when they are available.

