# • Devices Worn:

- Study pump
- Guardian™ Sensor (3)
- Guardian™ Link (3) transmitter

10813115DOC

	Study Period Synopsis (Visits 5-18)					
Overview:						
The study period is approximately 90 days long.						
	Study Period Device Procedures					
• Devic	ces Worn:					
0	Study pump					
0	Guardian™ Sensor (3)					
0	Guardian™ Link (3) transmitter					
Calib	ration Requirements with Study Meter:					
0	Approximately 30 minutes to 2 hours after the Guardian ™ Sensor (3) is initialized, the study pump will alert the user to enter a SMBG to perform initial calibration.					
0	After the first calibration, the user must calibrate the Guardian ™ Sensor (3) with the study meter within 6 hours of the first calibration. BG values from the study meter, which have been confirmed by subjects, will be used for calibrations.					
0	The user must calibrate via SMBG with the study meter when prompted by the study pump. BG values from the study meter, which have been confirmed by subjects, will be used for calibrations.					
0	The user must calibrate with the study meter every 12 hours after last calibration.					
0	Minimum of one calibration every 12 hours will be required with the study meter					
0	Best practices should be followed for each BG measurement (e.g. clean hands, "second drop" technique and accepting the calibration on the pump without delay)					
0	Other recommendations:					
	
 
Should always have clean dry fingers when checking blood glucose
 
					
	
 
Only fingertips should be used to obtain blood samples for calibration
 
					
Auto	Mode Settings:					
0	The Auto Mode (Closed Loop) setpoint for the closed loop algorithm:					

Medtronic

Page 54 of 118

10813115DOC

	The sponsor will provide guidance on the starting setpoint for subjects based on cohorts listed below:
	
 
A minimum of 50 subjects 14 years of age and older will start the study with an Auto Basal setpoint of 100 mg/dL. They will switch to the 120 mg/dL setpoint after 45 days (± 5 days) of the study period.
 
A minimum of 50 subjects 14 years of age and older will
 

	start the study with an Auto Basal setpoint of 120 mg/dL. They will switch to the 100 mg/dL setpoint after 45 days (± 5 days) of the study period.

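### The 72-hour FDA notice, 7-day CEC review and required CEC stop/continue recommendation are written for the study period only, so they do not reach continued access, where the 780G is used

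*Protocol*

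**What the plan says.** Protocol Section 9.12.2 covers three kinds of event: UADE, device-related DKA and device-related severe hypoglycemia. It opens with "During the study period, the following steps will be taken for" and lists four steps:

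1. The site tells the sponsor within about 24 hours.
2. The sponsor tells FDA within about 72 hours.
3. The CEC reviews the event within 7 days of the sponsor being notified.
4. The CEC makes a recommendation: (a) carry on, (b) stop enrolling but let enrolled subjects continue, or (c) "If the entire study must be stopped, including subjects who have already received study devices".

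Section 5 separates the two periods: "The study period will be approximately 90 days long. It will be followed by a continued access period". After run-in, "subjects will proceed to the study period, which begins at Visit 5", and Sections 9.1 and 9.3 end that period at Visit 18. In continued access, "all participating subjects will transition from the 670G system, version 4.0 AHCL, to the 780G system". Section 3.2 gives the reason: "during the continued access period, all remaining subjects will receive the 780G insulin pump system to evaluate subject safety".

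Where the protocol means both periods it names both. The safety endpoints in Sections 4.2.3 and 14.4.3 are headed "During Study Period and Continued Access".

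**The concern.** Read literally, the fastest whole-study safety response stops applying at the point where a new pump, sensor and transmitter come into use. A device-related severe hypoglycemia on the 670G at Day 60 starts the 72-hour notice, the 7-day review and a required CEC recommendation. The same event on the 780G starts none of the three.

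The events most affected are the expected ones. DKA and severe hypoglycemia are listed as pump, infusion-set or closed-loop risks in Table 3 (Section 10.1), and Section 11.7 treats a device-related event already identified in the protocol as anticipated. Such an event would normally not be a UADE unless its severity or incidence was unexpected (Section 11.2). The 10-working-day reporting limit in Section 11.5 would then not apply either. What is at stake is a prompt, required decision on whether subjects already wearing the 780G may go on using it.

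**Working it through.** No arithmetic beyond counting applies, and the plan gives no figure to reproduce. The check compares each step and trigger in Section 9.12.2 with what the rest of the protocol provides in continued access.

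**The four steps**

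| Step in 9.12.2 | What remains in continued access | Lost |
|---|---|---|
| 1. Site to sponsor, about 24 hours | Section 11.4: severe hypoglycemia, DKA, SAE and SADE, 24 hours desired, no period limit | Nothing material |
| 2. Sponsor to FDA, about 72 hours | Section 11.5: safety reports to FDA as regulations require, no time stated | The 72-hour deadline |
| 3. CEC review, 7 days | Section 12.1: CEC reviews these events without a period limit, but refers back to 9.12.2 for the 7-day requirement | The 7-day deadline |
| 4. CEC recommendation after each such event | Section 12.1: factors the CEC should weigh, including stopping the whole study. Section 12.2: the DMC may recommend stopping | The event that obliges a recommendation |

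Count: 1 step keeps its target time, 2 continue without their deadline, and 1 continues without its trigger (1 + 2 + 1 = 4). The gap is two deadlines and one trigger.

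**The three trigger events**

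- UADE: another dated rule applies, 10 working days to sponsor and IRB (Section 11.5).
- Device-related DKA, when anticipated: no other dated rule beyond the desired 24-hour site report.
- Device-related severe hypoglycemia, when anticipated: the same.

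So 1 of 3 keeps another dated rule and 2 of 3 normally do not.

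**Does anything else extend the steps?** Sections 9.12.1, 11.3-11.5, 12.1 and 12.2 do not, and the SAP has no stopping rule for either period. The synopsis repeats the steps, but in the text available its copy begins at step 1, without the opening line. Whether it carries the same limit is unknown. The finding is therefore that no visible text extends the steps.

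**What supports the 780G system.** Section 3.1 describes the pump algorithm as functionally equivalent to the one in the 670G version 4.0. The calibration-free sensor algorithm was characterized by applying it to raw data from a prospective investigation with YSI or SMBG reference values. Its use within the closed loop was assessed by in silico modeling.

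**The case against.** The strongest reply is that the substance of all four steps survives. Site reports, regulatory safety reports and CEC review carry no period limit. The DMC meets about every 90 days and ad hoc, follows rates of severe hypoglycemia, DKA and device-related events, and can recommend stopping for subjects who already hold devices. Section 9.3 adds adverse-event checks at Days 1, 3, 7, 15 and 30 after the 780G start. Sections 9.11 and 9.12.1 withdraw a subject after DKA or severe hypoglycemia, the latter section where the event is related to Auto Mode. All of this stands, and a reader who inferred that continued access is unsupervised would be wrong. None of these provisions, however, gives the CEC a deadline or obliges it to make a stop/continue recommendation after a single event. The one-week target for a DMC stopping recommendation (Section 12.2) runs from the DMC meeting, not from the event.

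A second reply concerns intent. The term is used loosely: the continued access synopsis in Section 9.1 has a sub-heading that refers to study period device procedures, and 9.12.2 itself is titled as a rule for the entire study. The limit may be leftover wording. That stands too, and the documents do not support inferring that the sponsor chose to exempt the 780G. It is also a reason to settle the text, since a site has only the wording to go by.

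Third, options (a) and (b) turn mainly on enrollment, and continued access takes only subjects who completed the study period. The limit could therefore be deliberate. Option (c) remains fully relevant.

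A reader might also infer that the 780G sensor algorithm rests on modeling alone. Section 3.1 does not support that, given the prospective reference data.

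**Conclusion.** The point holds in a limited form. As written, two explicit deadlines (72 hours to FDA, 7 days for CEC review) and one mandatory trigger (the CEC recommendation) do not apply in continued access. The effect falls mainly on anticipated device-related DKA and severe hypoglycemia.

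This rests on three assumptions: that study period has the meaning given in Sections 5, 9.1 and 9.3; that the missing opening line of the synopsis copy does not say otherwise; and that the sponsor would class these events as anticipated under Section 11.7.

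The size is a count of provisions. The documents set no CEC deadline in continued access and do not state exposure there, so neither a delay nor a number of affected events can be derived. They do not show that any event would be handled late or unsafely. This is a cheap improvement for patient safety.

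**What to change.** Change the opening limit of Section 9.12.2 to *During the study period and the continued access period*, leaving the rest of the line and the four steps as they are. Check the synopsis copy and align it if it carries the same limit. Add a note that option (c) is the relevant choice in continued access. If continued access is meant to be exempt, state that and give the reason.

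The cost is one phrase in a protocol amendment. Under Section 16.7 a significant amendment goes to the IRBs and, where applicable, to the regulator, so it is best bundled with the next one. A few more events would come under the 72-hour and 7-day clocks. The CEC already reviews those events without a period limit, so the added burden is mainly timing.

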# 10. Risks and Benefits

# **10.1. Potential Risks**

# Table 3. Risks, Prevention and Mitigation

Risks with Infusion Sets	Prevention and Mitigation

 
Risks with infusion sets may include:
 
Localized infection
 
Skin irritation/redness
 
Bruising
 
Discomfort/pain
 
Bleeding
 
Irritation
 
Rash
 
Hyperglycemia secondary to infusion set occlusion or infusion site failure including DKA
 
Hyperglycemia secondary to site falling off including DKA
 
Anxiety associated with insertion
 
	
 
Prevention and mitigation include:
 
Follow the provided user guides for insertions and care of infusion sets.
 
If an infusion site becomes irritated or inflamed, the infusion set will be removed and another placed in a new location.
 
In case of hyperglycemia secondary to infusion set occlusion, remove current infusion set and replace with new infusion set and give correction insulin if needed with syringe.
 
Follow the provided user guides for insulin pump management.
 
Train prior to study device use on appropriate device use and diabetes management principles and instruct to call investigator with problems.
 

Risks with Insulin Administration and Pumps	Prevention and Mitigation
Risks with the use of an insulin infusion pump may include the risk of malfunction of the components of the system (pump, software, infusion set and reservoir) as well as the risk of use error during use of the system. Device deficiencies or use errors can result in administration of too much or too little insulin which can lead to the following clinical consequences: 
 
Hypoglycemia
 
Hyperglycemia
 
Diabetic ketoacidosis
 
Severe hypoglycemia with or without associated seizure, coma or death
 
Kinked cannula leading to hyperglycemia
 
Infusion set disconnection from pump leading to hyperglycemia
 
Subject removes the reservoir from the pump but forgets to disconnect the infusion
 
	
 
Prevention and mitigation include:
 
Follow the provided user guides & instructions for insulin pump management which includes information on infusion set change.
 
Train prior to study device use on appropriate device use and diabetes management principles and instruct to call investigator with problems.
 
Instruct to check their meter glucose if their high or low symptoms do not match their sensor alerts or sensor glucose readings in order to make diabetes treatment decisions.
 
Instruct to check their meter glucose if there are any concerns that the sensor glucose value is not accurate.
 
Instruct to change infusion set if suspected catheter occlusion or administer insulin with syringe for persistent hyperglycemia especially if
 

This document is electronically controlled *Medtronic Business Restricted* 056-F275, vB Clinical Investigation Plan Template

10813115DOC Ve	rsion D	Page 71 of 118		Medtronic

 
Dislodged cannula leading to hyperg
 
A pump error may lead to under deliover-delivery of insulin
 
Battery failure – no insulin delivered
 
Insulin deterioration leading to hyperglycemia
 
Incomplete priming; fails to prime trand/or cannula, leading to hypergly
 
Remove a reservoir, without suspentive reconnecting after a while resulting Hypoglycemia
 
Patient not filling pump reservoir wheneeded leading to hyperglycemia
 
Magnetic Resonance Imaging result pump/transmitter malfunction
 
Inaccurate insulin delivery due to sualtitude changes.
 
Hypoglycemia or hyperglycemia frommanual bolus
 
Hypoglycemia or Hyperglycemia from use of the AHCL Auto Mode feature sensor glucose values may be used calculate insulin bolus amounts
 
	
 
set from the body which results in hypoglycemia or severe hypoglycemia
 
Dislodged cannula leading to hyperglycemia
 
A pump error may lead to under delivery or over-delivery of insulin
 
Battery failure – no insulin delivered
 
Insulin deterioration leading to hyperglycemia
 
Incomplete priming; fails to prime tubing and/or cannula, leading to hyperglycemia
 
Remove a reservoir, without suspending and reconnecting after a while resulting in a Hypoglycemia
 
Patient not filling pump reservoir when needed leading to hyperglycemia
 
Magnetic Resonance Imaging resulting in pump/transmitter malfunction
 
Inaccurate insulin delivery due to sudden altitude changes.
 
Hypoglycemia or Hyperglycemia from manual bolus
 
Hypoglycemia or Hyperglycemia from the use of the AHCL Auto Mode feature where sensor glucose values may be used to calculate insulin bolus amounts
 
Hypoglycemia or hyperglycemia from
 
		ill be trained gement	

 
Risks with hyperglycemia may include
 
Diabetic ketoacidosis
 
Symptomatic ketosis
 
Cardiovascular event
 
Dehydration
 
Potassium and sodium imbalance
 
Shock
 
Altered mental status
 
Coma
 
Acidosis
 
	Preve	
 
management.
 
Parent(s)/guardian(s)/comp present at night with subject on study device and diabeted principles and instructed to problems.
 
Train prior to study device u device use and diabetes ma and instruct to call investiga Instruct to check their metechigh symptoms do not matco or sensor glucose readings i diabetes treatment decision
 
Instruct to check their metechigh symptoms that the sensor not accurate.
 
	eanion(s) ts and w es manag call inves use on ap nagemer ator with er glucose th their so in order t s. er glucose or glucose	will be vill be trained gement stigator with propriate nt principles problems. e if their ensor alerts to make e if there are e value is cose levels

10813115DOC	Version D	Page 72 of 118		Medtronic
Risks with hypoglycemia may include: 
 
Seizure
 
Coma
 
Altered mental status
 
Loss of consciousness
 
Cardiovascular event
 
Death
 
Risk of rebound hyperglycemia
 
		
 
Prevention and mitigation include:         
 
Follow the provided user guides for insulin p management.
 
Parent(s)/guardian(s)/companion(s) will be present at night with subjects and will be trae on study device and diabetes management principles and instructed to call with problem
 
Train prior to study device use on appropriat device use and diabetes management principles and instruct to call investigator with problem
 
Instruct to check their meter glucose if their symptoms do not match their sensor alerts or sensor glucose readings in order to make diabetes treatment decisions.
 
Instruct to check their meter glucose if there any concerns that the sensor glucose value not accurate.
 
Instruct to have glucose on hand for hypoglycemia
 
 
 
		
Risk with Sensors	Pr	evention and Mitigation		
Risks with Sensors may include:         Skin irritation or reaction to adl         Bruising         Discomfort         Redness         Bleeding         Excessive bleeding due to antice         Pain         Rash         Infection         Irritation from tapes used with sensing products         Raised bump         Appearance of a small "freckle-where needle was inserted         Allergic reaction         Syncopal episode secondary to insertion         Soreness or tenderness         Swelling at insertion site         Sensor fracture, breakage or date meedle removal         Residual redness associated with and or tapes         Scab         Blister         Itchiness         Infermation	nesives oagulants glucose- like" dot needle amage ed with sensor	
 
evention and mitigation include:
 
Follow the provided user gui and care of sensors.
 
If a sensor site becomes infe the sensor will be removed a in a new location
 
Instruct to check their meter high or low symptoms do no alerts or sensor glucose read make diabetes treatment de
 
Instruct to check their meter any concerns that the senso not accurate.
 
Instruct if there are no sense treatment decisions will be n confirmed.
 
	ected or and anot r glucose ot match dings in o cisions. r glucose r glucose or values	inflamed, her placed e if their their sensor order to e if there are e value is 5, no

Inflammation

Anxiety

•
10813115DOC Version D	Page 73 of 118 Medtronic

 
Incorrect sensor glucose reading results in incorrect diabetes management
 
Subject over-treating secondary to alarms which can result in hyperglycemia or hypoglycemia
 
Anxiety associated with insertion
 
	
Risks with Transmitter	Prevention and Mitigation

 
Risks with Transmitter may include:
 
Skin irritation or reaction to adhesives
 
Bruising
 
Discomfort
 
Redness
 
Pain
 
Rash
 
Infection
 
Irritation from tapes used with glucose-sensing products
 
Raised bump
 
Allergic reaction
 
Soreness or tenderness
 
Residual redness associated with adhesive and/ or tapes
 
Scab
 
Blister
 
Itchiness
 
Inflammation
 
	
 
Prevention and mitigation include:
 
Follow the provided user guides.
 
Train on the proper use of the transmitters.
 

Risks with Serter	Prevention and Mitigation

 
Risks with serters may include:
 
Improper insertion may lead to device performance issue or hyperglycemia
 
	
 
Prevention and mitigation include:
 
Follow the provided user guides for insertions and care of device.
 
Train on the proper use of the serter and skin preparation prior to insertion.
 

Risks with Finger Sticks	Prevention and Mitigation

 
Risks with frequent finger stick testing may include:
 
Potential risks associated with frequent meter testing of blood glucose and blood ketones include discomfort and ecchymosis at tips of fingers
 
Potential risks associated with finger stick testing include discomfort and bruising
 
	
 
Prevention and mitigation include:
 
Follow the provided user guides for use of the study meter(s) with fingerstick testing.
 
Train on the proper use of the study meter(s) and fingerstick testing.
 

10813115DOC

Page 74 of 118

Risk with Closed Loop Therapy	Prevention and Mitigation

 
Risks with Closed Loop may include: 
 
Hypoglycemia
 
Severe hypoglycemia
 
Diabetic ketoacidosis
 
 
 
User Entry Error 
 
Patient administering boluses by entering false carb doses leading to hypoglycemia or hyperglycemia
 
Patient entering false glucose values for any reason leading to hypoglycemia and hyperglycemia
 
Patient entering false BG values for calibration leading to hypoglycemia or hyperglycemia
 
Sensor failure resulting from patient failure to calibrate leading to hypoglycemia or hyperglycemia
 
Sensor over-reading resulting in hypoglycemia
 
Sensor over-reading resulting in hypoglycemia
 
Sensor nissed transmission, or any other fault resulting in no SG value, leading to hypoglycemia
 
Voluntary insulin delivery (with the pump or with a syringe) immediately prior to entering Auto Mode may result in severe hypoglycemia despite shutting down insulin delivery by the algorithm
 
Hypoglycemia or hyperglycemia related to entering or exiting Closed Loop(Auto Mode)
 
Hypoglycemia or hyperglycemia related to entering or exiting Closed Loop(Auto Mode)
 
 
 
	
 
Prevention and mitigation include:
 
Follow the provided user guides for insulin pummanagement.
 
Train prior to study device use on appropriate device use and diabetes management principles and instruct to call investigator with problems.
 
Instructed to check their meter glucose if their high or low symptoms do not match their sensor alerts or sensor glucose readings in order to make diabetes treatment decisions.
 
Instructed to check their meter glucose if there are any concerns that the sensor glucose value is not accurate.
 
Instructed if there are no sensor values, no treatments decision will be made until a BG is confirmed.
 
Instruct to have glucose on hand for hypoglycemia
 
Instructed to use additional BG meter readings (they are not to calibrate with those readings) to verify their glucose levels.
 
If acetaminophen is taken, subjects will be instructed to use the temp target feature (wher used, Auto Correction is not available)
 
Instruct subjects that in case of prolonged use of acetaminophen, the temp target feature can be used repeatedly and in succession
 

10813115DOC	Version D	Page 75 of 118	Medtronic
Risks with hyperglycemia may Diabetic ketoacidosis Symptomatic ketosis Cardiovascular event Dehydration Potassium and sodium Shock Altered mental status Coma Acidosis	n imbalance	
 
Prevention and mitigation include:
 
Follow the provided user guides for insulin pumanagement.
 
Train prior to study device use on appropriate device use and diabetes management principl and instruct to call investigator with problems
 
Instruct to check their meter glucose if their h symptoms do not match their sensor alerts or sensor glucose readings in order to make diabetes treatment decisions.
 
Instruct to check their meter glucose if there any concerns that the sensor glucose value is not accurate.
 
Instruct if there are no sensor values, no treatments decision will be made until a BG is confirmed.
 
	
Risks with hypoglycemia may Seizure Coma Altered mental status Loss of consciousness Cardiovascular event Death Risk of rebound hyper		confirmed.         Prevention and mitigation include:         • Follow the provided user guides for insulin management.         • Train prior to study device use on appropridevice use and diabetes management prime and instruct to call investigator with proble         • Instruct to check their meter glucose if the symptoms do not match their sensor alerts sensor glucose readings in order to make diabetes treatment decisions.         • Instruct to check their meter glucose if the any concerns that the sensor glucose value not accurate.         • Instruct if there are no sensor values, no treatment decisions will be made until a BO confirmed.         • Instruct to have glucose on hand for hypoglycemia	
Risk with Acetaminophen U	lse Pre	evention and Mitigation	


acetaminophen active may be different for e

Liver damage, liver fai fatal liver failure can c

	sor glucose readings an over-delivery of se hypoglycemia. The pends on the amount of in subject's body and ach subject ilure and/or rare but occur us and potentially fatal een reported iding those which are y fatal can occur	
 
evention and mitigation include:
 
Follow the user guide
 
Instruct to avoid the user of acetaminophen
 
If acetaminophen is taken instructed to use additional (they are not to calibrate verify their glucose levels
 
If acetaminophen is taken SmartGuard™ feature is a instructed to use the temp used, Auto Correction is n
 
Instruct subjects that in c acetaminophen, the temp used repeatedly and in su
 
	, subjects will be al BG meter readings with those readings) to , while the ctive, subjects will be o target feature (when ot available) ase of prolonged use of target feature can be

- Kidney disease
- Lowered blood counts (red cells, and white •

used repeatedly and in succession

CIP321 Clinical Investigation Plan			
10813115DOC	Version D	Page 76 of 118	Medtronic
cells)			

